##### Development of steroid dependent nephrotic syndrome (according to KDIGO criteria)

- This categorical outcome will be analyzed with either the Pearson chi-squared or Fisher exact test.

##### Cumulative dosage of prednisolone during study period

- Depending on the distribution of the data, this will be analyzed with either the *t* test or the Mann-Whitney test.

### **Missing data**

Missing baseline and outcome data will not be imputed. We will state which data are missing and calculate frequencies using the total number of patients with available data. When a patient is lost to follow-up or has withdrawn consent, we will use all available data up until

withdrawal of consent or loss to follow-up.

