### Analysis populations

The main analysis will consist of an intention-to-treat analysis. Participants who are lost to follow-up or in whom trial medication is stopped prematurely will be analyzed according to their allocated groups. In addition, as intention-to-treat analysis may increase the risk of type 1 errors in a non-inferiority trial, a per-protocol analysis will also be conducted.[5]

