### Withdrawal/follow-up

Patients randomised who did not take their allocated treatment will be considered as having deviated from the protocol. Their data will be included in both the intention-to-treat and per-protocol analyses. If a patient or their representative withdraws consent for data collection, only data up to the point of withdrawal will be used in the analysis.

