### **Analysis methods**

#### Primary endpoint

##### Time to first relapse after the final prednisolone dose

- As normal distribution is not assumed, the median time to relapse will be compared between the groups using a Mann-Whitney test;
- In case patients did not experience any relapse after 24 months or patients are lost to follow up before they experienced a relapse, incidence rates or person-time rates will be used to compare the groups;
- If a normal distribution is shown in the Shapiro-Wilk W test, a *t* test will be used;
- The percentages of study subjects with a relapse at 12 and 24 months will be compared between the groups;
- The cumulative probability on the absence of a relapse will be estimated by survival analysis, according to the Kaplan-Meier method. Log-rank tests are used for the comparison between the standard treatment group and placebo group;
- To test for the influence of factors, such as the use of maintenance immunosuppressive therapy, logistic regression analysis for nephrotic syndrome relapses with covariate analysis will be performed;
- Within each subject time to relapse after study medication will be compared to time to relapse before entering the study using a paired sample *t* test. This test will exclusively be performed in patients without changes in maintenance therapy.

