##### Development of frequent relapsing nephrotic syndrome (according to KDIGO criteria)

- This categorical outcome will be analyzed with either the Pearson chi-squared or Fisher exact test.

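### Progression, cumulative prednisolone and the crude relapse percentages are compared without regard to length of follow-up, so their results depend on how many children leave early and when

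*SAP*

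**What the plan says.** **Who is kept, and with what data.** SAP, Analysis populations: "Participants who are lost to follow-up or in whom trial medication is stopped prematurely will be analyzed according to their allocated groups". SAP, Withdrawal/follow-up, on withdrawn consent: "only data up to the point of withdrawal will be used in the analysis". SAP, Missing data: "Missing baseline and outcome data will not be imputed"; the plan will "calculate frequencies using the total number of patients with available data"; and "When a patient is lost to follow-up or has withdrawn consent, we will use all available data up until" withdrawal or loss.

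**How the outcomes are compared.**
- Frequent relapsing disease: "This categorical outcome will be analyzed with either the Pearson chi-squared or Fisher exact test". The same sentence is given for steroid dependent disease.
- Cumulative prednisolone: "Depending on the distribution of the data, this will be analyzed with either the" *t* test or the Mann-Whitney test. Its measurement value is a total in mg/m².
- Relapse percentages, listed under the primary endpoint: "The percentages of study subjects with a relapse at 12 and 24 months will be compared between the groups". No test, denominator or rule for leavers is given.
- Number of relapses: Poisson regression for relapse rates, with no offset stated.
- Time to first relapse: person-time rates when children are lost or relapse-free, plus Kaplan-Meier and log-rank.

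**What the definitions promise.** Under Secondary outcomes, both progression outcomes are described as censored at 24 months, and cumulative prednisolone as censored at 12 and 24 months.

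**The concern.** The definitions speak of censoring, but a chi-squared, Fisher, *t* or Mann-Whitney test on a yes/no status or a total cannot use a censoring time. A child observed for three months and a child observed for 24 months carry the same weight, although the first had far less time to meet a progression criterion or to receive prednisolone for further relapses. The plan recognises this for time to first relapse and provides for it there. It makes no such provision for progression, for the prednisolone total or for the crude percentages.

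These outcomes matter in a steroid-reduction trial. They show whether the shorter course saves prednisolone over 24 months, and whether it does so without more children progressing. If they move with dropout, a difference in loss between arms can pass for a treatment effect, and a real difference can be understated.

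**Working it through.** **The plan's own figures.** The SAP states no dropout rate, so there is no figure on loss to reproduce. The 72 per group (Sample size) is used below only as the arm size. It reproduces from SD 120 days, margin 50 days, 80% power and one-sided 5%: 2 × (1.645 + 0.842)² × (120/50)² = 71.2, rounded up to 72.

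**Step 1: what the rules allow for a leaver.**
- *Counted in full with data to date.* This is the likeliest reading of using all available data by allocated group. Events and doses after departure are read as absent.
- *Dropped only if event-free at departure*, because the 24-month status is unknown. Those who met the criterion before leaving stay, so the percentage is too high. This does not apply to prednisolone, which has no event to keep.
- *All leavers dropped.* Under non-informative loss this gives no bias, but it contradicts using data up to the point of loss.

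**Step 2: assumptions (illustrative; none is from the SAP unless stated).** A fraction *d* of an arm leaves, uniformly over 24 months and independently of outcome. Event times are uniform over 24 months and dose accrues evenly. The true progression risk is *p* = 50% in both arms. That value is borrowed from Sample size, where half of relapsing children go on to frequent relapsing disease; it is not a stated 24-month trial risk.

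**Step 3: leavers counted in full.** A leaver is observed for half the period on average, so:
- observed proportion = *p*(1 − *d*/2)
- observed mean dose = true mean × (1 − *d*/2)

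For 20% v 5% loss, the dose ratio is (1 − 0.10)/(1 − 0.025) = 0.90/0.975 = 0.92, about 8% less with no treatment effect. Progression is 0.5 × 0.90 = 45.0% v 0.5 × 0.975 = 48.75%, a false gap of 3.75 points.

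| Loss, arm 1 v arm 2 | Observed progression, true 50% v 50% | Dose ratio, arm 2 / arm 1 (true 1.00) | Observed gap if true risks are 50% v 60% |
|---|---|---|---|
| 0% v 0% | 50.0% v 50.0% | 1.00 | 10.0 points |
| 10% v 10% | 47.5% v 47.5% | 1.00 | 9.5 points |
| 5% v 15% | 48.75% v 46.25% | 0.95 | 6.75 points |
| 5% v 20% | 48.75% v 45.0% | 0.92 | 5.25 points |
| 0% v 20% | 50.0% v 45.0% | 0.90 | 4.0 points |

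Last column, last row: 0.60 × 0.90 − 0.50 = 0.04. If the progression criteria tend to be met late in follow-up, more events fall after departure and the loss is larger than shown.

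**Step 4: only event-free leavers dropped.** Observed proportion = *p*(1 − *d*/2) / [1 − *d*(1 − *p*/2)].
- *d* = 20%: 0.45 / (1 − 0.20 × 0.75) = 0.45/0.85 = 52.9%
- *d* = 5%: 0.4875 / (1 − 0.05 × 0.75) = 0.4875/0.9625 = 50.6%

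Both exceed the true 50%, and the arm losing more now looks worse by about 2.3 points.

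**Step 5: effect on the test.** Simulation under the Step 2 assumptions, leavers counted in full, 72 per arm, 20,000 trials, uncorrected chi-squared at two-sided 5%, no true difference. Rejection rates were about 5.5% (10% v 10% loss), 6.5% (5% v 15%) and 9.4% (0% v 20%).

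Under the same assumptions, a time-to-event or exposure-adjusted analysis targets the true 50% v 50% and a dose ratio of 1.00.

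**The case against.** **The denominator sentence may exclude leavers.** The plan bases frequencies on patients with available data, which could be read as leaving out children with incomplete follow-up. This stands in part. A reader might infer that leavers are certainly treated as followed for 24 months, but the SAP does not say so. It does not define the denominator at all. Dropping every leaver would remove the bias under non-informative loss, but it conflicts with using data up to departure.

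**Relapse counts use a rate model.** This stands. Number of relapses is not compared by the tests at issue. Poisson regression of rates is the usual vehicle for exposure time, so the missing offset needs clarification and is not an error. Time to first relapse is protected by the person-time, Kaplan-Meier and log-rank analyses.

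**No noninferiority conclusion is touched.** This also stands. One might infer that dilution favours a finding of no worse, but the only margin (50 days, Sample size) is on time to relapse. No secondary outcome has a margin.

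**The sizes are assumed and modest.** This stands as a limit on size. Large imbalance is not a given in a double-blind trial, and equal non-informative loss produces no false difference. With 72 per arm and 50% risk, the standard error of a difference is √(2 × 0.5 × 0.5/72) = 8.3 points, well above the 3.75-point gap. The gap is nonetheless systematic and avoidable at little cost.

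**The better methods also assume non-informative loss.** True. They remove the effect of unequal observation time, but not that of loss related to outcome.

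**Conclusion.** The concern holds for the two progression outcomes, cumulative prednisolone, and the crude 12- and 24-month relapse percentages. The plan keeps partial follow-up, calls the three secondary outcomes censored, then compares them by methods that cannot take censoring into account. It also leaves the denominator for leavers undefined.

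The direction is not fixed. Counting leavers in full flatters the arm with more loss; dropping only event-free leavers makes its percentages look worse. Equal loss, with leavers counted in full, lowers both arms and dilutes a true difference.

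Under assumed uniform, non-informative loss of 20% v 5%, the arm losing more shows about 8% less cumulative prednisolone and 3.75 points less progression (true risk 50%) with no treatment effect. These are illustrations, because the SAP gives no dropout rate.

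A reader might also infer that a child who leaves relapse-free contributes zero prednisolone. That is not generally so, since Eligibility admits children on low-dose alternate-day maintenance prednisolone. The change should be made, but the primary survival analyses do not depend on it.

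**What to change.** - **Frequent relapsing and steroid dependent disease:** analyse time to first meeting each criterion, censored at withdrawal or loss. Report Kaplan-Meier 24-month estimates by arm and their difference with a 95% CI.
- **Cumulative prednisolone:** compare dose per unit of follow-up (total mg/m² over total person-time, by arm) with a robust or bootstrap CI. State that this treats the dosing rate as roughly constant over follow-up.
- **Relapse percentages at 12 and 24 months:** take them from the Kaplan-Meier curves already planned.
- **Number of relapses:** state log follow-up time within the period as the Poisson offset (a clarification).
- **Missing data:** say who counts as having available data for any frequency that is still reported.

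The blind review after database lock (Blinding), which may still amend the SAP, is the latest suitable moment, because the final analyses follow unblinding.

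**Cost:** SAP wording and a little programming. SPSS should cover all of it except possibly the bootstrap interval. The dates of relapse, withdrawal and last contact are already needed for time to first relapse. The remaining downside is that these methods still assume non-informative loss, so reasons for and timing of loss should be reported by arm.

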### **Interim analysis**

The total inclusion of 144 patients is expected to be finalized in 1.5 years, thereby the DSMB meeting will take place approximately 8 months after the start of inclusion. The mean follow-up period of the 40 patients at that time will be 5.5 (range 3-8) months. Previous literature shows a cumulative incidence rate of a first relapse of 30% after 5.5 months.[3] As the placebo group will receive approximately 35% less prednisolone during the study period, we based the power calculation on a difference of maximum 1/3rd earlier until the first relapse after study medication. Therefore we would like to advise the DSMB to check whether the patients with a relapse are in group A or B (dummy groups) if over 8 patients have experienced a relapse at interim analysis. Aim is then to check for a significant difference in relapse rate between the two groups. If there seems to be a significant difference between the two groups and the percentage of patients with a relapse in either one or both groups exceeds 40% than they might consider to unblind the groups.

### **Harms**

Information on adverse events will be collected by means of reported adverse events in the questionnaires and spontaneous reports from patients and caregivers. The number of adverse events, serious adverse events and suspected unexpected serious adverse reaction will be compared between the two arms using a chi-squared test (or Fisher's exact test), with risk ratios and 95% confidence intervals when these are computable. For all continuous variables either means with standard deviation or medians with interquartile range will be calculated where appropriate and testing for difference will be performed with either the *t* test or Mann-Whitney test where appropriate.

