## **INTRODUCTION**

### **Background and rationale**

The first-line treatment for idiopathic nephrotic syndrome in children is oral corticosteroids.[1] Most children experience several relapses of nephrotic syndrome, needing repeated courses of corticosteroid therapy or even more aggressive treatment with other immunosuppressive drugs. For most children, long-term prognosis is for complete resolution of their disease over time with maintenance of normal kidney function. Therefore, it is vital to focus on minimizing adverse events of the disease and its treatment. The aim of the RESTERN study (REducing STERoids in Relapsing Nephrotic syndrome) is to assess the safety and effectiveness of a reduced alternate day steroid schedule for treatment of a nephrotic syndrome relapse in comparison with the current standard therapy.

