### **Sample size**

From previous studies, we know the incidence of nephrotic syndrome in Dutch children to be 1.52/100,000 children/year.[2] Eighty percent of the pediatric patients develop at least 1 relapse of whom 50% continue towards frequent relapsing nephrotic syndrome. Based on data from previous studies, average time to relapse in the first year is approximately 185 days (standard deviation of 120 days).[3] Using the power calculation for a noninferiority trial with a continuous primary outcome, a power of 80% and a noninferiority limit of 50 days, 72 patients per group are required. Using a Cox Proportional Hazard time-to-relapse analysis (survival analysis)[4], similar numbers can be calculated.

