### **Timing of interim analysis and stopping guidance**

Interim analysis will be performed by the Data Safety and Monitoring Board (DSMB), three months after inclusion of the first 40 participants. The study will be terminated in a premature stage if the safety of participants is jeopardized. As the placebo group only receives less active medication (in comparison with the standard treatment group), the occurrence of any serious adverse event is considered highly unlikely. The only risk may be found in the primary outcome of the study, i.e. significant inferiority of the placebo-treatment schedule with regards to time to next nephrotic syndrome relapse.

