## **STATISTICAL PRINCIPLES**

### **Level of confidence intervals and p-values**

For this noninferiority trial, the upper bound of the 2-sided 95% confidence interval for the treatment effect has to be below the margin to declare that noninferiority has been shown. P-values <0.05 will be considered statistically significant.

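### The harms analysis names no effect measure or interval for use when the risk ratio cannot be computed, so rare serious events may be reported without any bound on excess risk (minor reporting weakness)

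*SAP*

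**What the plan says.** The Harms section lists three categories: "The number of adverse events, serious adverse events and suspected unexpected serious adverse reaction". For each, the arms are tested against one another by chi-squared or by Fisher's method. Estimates accompany the test in this form: "with risk ratios and 95% confidence intervals when these are computable". The section gives no rule for choosing between the two tests, no interval method, and no other effect measure for cases where the ratio or its interval is unavailable. It sets no criterion for concluding that the reduced schedule is safe.

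Three other places bear on this:

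- Background and rationale gives the study's aim as "to assess the safety and effectiveness of a reduced alternate day steroid schedule".
- Timing of interim analysis and stopping guidance argues that the study arm only receives less active drug, so that "the occurrence of any serious adverse event is considered highly unlikely". It gives no numerical rate.
- Level of confidence intervals and p-values bases the noninferiority decision on an interval: "the upper bound of the 2-sided 95% confidence interval for the treatment effect has to be below the margin". For tests in general, "P-values <0.05 will be considered statistically significant".

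**The concern.** A risk ratio of reduced to standard schedule is undefined when the standard arm has no events. When only the reduced arm has none, the ratio is 0 and the usual log-scale interval fails. When neither arm has any, neither quantity exists. The SAP anticipates this and deals with it by leaving the estimate out.

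The omission falls on serious events and suspected unexpected serious reactions, the categories where the SAP itself expects very few events. For these, the only inferential result promised is a p-value. A p-value from sparse counts does not say how large an excess the data still allow, and that is what a reader needs in order to judge safety. An interval for the risk difference exists for every table, including 0 v 0.

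**Working it through.** **Inputs.** The Harms section contains no figure to reproduce. The arm size comes from Sample size: "a power of 80% and a noninferiority limit of 50 days, 72 patients per group are required". That number can be recovered as n = 2(z₁₋α + z₀.₈₀)² × 120² / 50². With one-sided α = 0.05 this is 11.52 × (1.645 + 0.842)² = 71.2, so 72. (With one-sided 0.025 it is 90.4, so 91. That discrepancy is a separate matter; 72 serves here only as the arm size.) I assume that 72 per arm are analysed and that each child is scored yes or no for at least one event. Event risks are assumed at 0.5%, 1% and 2%.

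**How often is an arm empty?** With the same risk p in both arms, let q = (1 − p)^72. Then P(at least one empty arm) = 1 − (1 − q)², P(both empty) = q², and P(only the standard arm empty) = q(1 − q).

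| p | q | at least one empty | both empty | only standard empty |
|---|---|---|---|---|
| 0.5% | 0.697 | 91% | 49% | 21% |
| 1% | 0.485 | 73% | 24% | 25% |
| 2% | 0.233 | 41% | 5% | 18% |

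The remaining share, only the reduced arm empty, equals the last column by symmetry.

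**What does the p-value say?** Two-sided tests of 0/72 (standard) v k/72 (reduced):

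| k | Fisher p | uncorrected chi-squared p |
|---|---|---|
| 3 | 0.245 | 0.080 |
| 4 | 0.120 | 0.043 |
| 5 | 0.058 | 0.023 |
| 6 | 0.028 | 0.012 |

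At k = 4 and k = 5 the two permitted tests fall on opposite sides of 0.05. Expected counts there are 2.0 and 2.5 events per arm, where Fisher is the usual choice, but the SAP does not fix this.

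**What would an interval add?** Newcombe's 95% interval combines the Wilson limits of the two arms. Let d = k/72, let (l₁, u₁) be the Wilson limits for k/72, and let (l₂, u₂) be those for 0/72, which are 0 and 5.07%.

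- Lower limit = d − √[(d − l₁)² + u₂²]
- Upper limit = d + √[(u₁ − d)² + (0 − l₂)²], which reduces to u₁ because l₂ = 0

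For k = 5: d = 6.94%, l₁ = 3.00%, u₁ = 15.25%. The lower limit is 6.94 − √(3.94² + 5.07²) = 6.94 − 6.42 = 0.5 points. The upper limit is 15.2 points.

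| Events, standard v reduced | risk difference (points) | 95% Newcombe interval |
|---|---|---|
| 0 v 0 | 0.0 | −5.1 to 5.1 |
| 0 v 3 | 4.2 | −1.6 to 11.5 |
| 0 v 5 | 6.9 | 0.5 to 15.2 |

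The SAP as written commits to none of these intervals.

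**The case against.** Restricting ratios to computable cases is an ordinary caveat and contradicts nothing in the SAP. The SAP places the main risk of the reduced schedule in the primary outcome, which has an interval-based rule and data monitoring board review, and no listed objective is a formal safety hypothesis. Event numbers by arm would presumably be visible, so a reader could derive an interval. The SAP names no interval method, so exact or score limits for the ratio are not ruled out. An empty reduced arm still leaves a computable ratio of 0. All of this stands, and it keeps the point minor. It does not supply a prespecified interval for the empty-arm case.

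A reader might go further and infer that the SAP will take a non-significant Fisher test as evidence of safety, or that this test will miss most relevant excesses. The document supports neither:

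- It sets no safety decision rule and does not make Fisher the only test.
- It gives no serious-event rate and no threshold for a relevant excess. Under assumed rates, Fisher's power is 15% for 0% v 5% but 74% for 0% v 10%, so any statement about missed harm depends on the rates chosen.
- Low power for rare events comes from having 144 children, not from the wording on ratios.

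The proposed interval can also disagree with the test. At 0 v 5 it excludes zero while Fisher gives p=0.058. That is a real cost, and the plan should say which of the two is the main summary.

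**Conclusion.** The point holds as a minor weakness in harms reporting. For the rarest and gravest categories the SAP may deliver a p-value and no bound on excess risk, although bounds of about 5, 12 and 15 points (0 v 0, 0 v 3 and 0 v 5) could be stated from the same data. How often this arises depends on the assumed risks of 0.5% to 2%, equal in both arms, and on 72 analysed per arm. The 41% to 91% range counts every trial with an empty arm. The narrower case of an empty standard arm with at least one event on the reduced schedule accounts for about 18% to 25%. The primary conclusion is not affected.

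**What to change.** Replace the qualifying clause in Harms with wording such as: for each harm category, the number and proportion of children with at least one event will be given per arm, with the risk difference (reduced minus standard) and its two-sided 95% Newcombe or Miettinen-Nurminen interval, including when one or both arms have no events; risk ratios will be added where computable; the interval is the main summary and the test is descriptive.

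The cost is a short change of wording and a standard calculation on data already collected. The downsides are visibly wide intervals for rare events and occasional disagreement with Fisher's test, which the last clause settles in advance. The change shows the uncertainty but does not reduce it.
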